1.6. Risk-Benefit Assessment

FAC is a rare disease, that leads to significant morbidity and mortality. There are no approved therapies and patients are currently managed with supportive care aimed at alleviation of heart failure symptoms. Clinical experience with ALN-TTRSC indicates that ALN-TTRSC is well-tolerated at fixed doses of 500 mg and results in a reduction in serum levels of TTR of >85%. The hypothesis is that a reduction of mutant and WT TTR amyloid deposition in the heart will lead to clinical benefit in these patients.

1.6.1. Injection Site Reactions

ISRs have been observed in subjects receiving ALN-TTRSC in clinical studies. The majority have been mild or moderate in severity. Typically, the reactions consist of localized erythema, pain, swelling, pruritus, or rash at or around the injection site, and are transient in nature. Occasionally, these reactions have been of longer duration, more severe in nature and/or recurrent. In some subjects, this resulted in discontinuation of ALN-TTRSC. If such reactions occur, rotation of the injection site (e.g., to the extremities) is recommended as a potential mitigation strategy (see Section 6.5). Dose reduction may be considered in some cases after consultation with the Medical Monitor (see Section 6.6).

1.6.2. Abnormal Liver Function Tests

Elevations of ALT and/or AST have been seen in subjects receiving ALN-TTRSC in completed and ongoing clinical studies. The majority of abnormalities have been mild and transient elevations of ALT and/or AST <3×ULN, and are not associated with changes in total bilirubin or clinical symptoms. In some subjects, higher ALT and/or AST elevations have been observed and led to interruption or discontinuation of study treatment. Serious hepatic adverse events have also been reported, including a case of possible drug-induced hepatitis and cholestasis; in this case a contributory role of study drug could not be excluded.

The risk of liver toxicity is lowered by requiring patients to have adequate liver function at study entry, as well as regular monitoring of LFTs during the study. If a patient develops clinical signs or symptoms such as unexplained anorexia, fatigue, jaundice, or dark urine, the Investigator should consider liver injury as a potential etiology.

Dose reduction may be considered in some cases after consultation with the Medical Monitor (see Section 6.6).

1.6.3. Vitamin A Lowering

The suppression of serum levels of TTR and RBP is expected to result in the lowering of circulating vitamin A levels. Preclinical and clinical data have shown that the lowering of circulating vitamin A associated with suppression of RBP does not result in severe vitamin A deficiency. Furthermore, there are individuals with RBP/TTR mutations who have life-long low levels of circulating vitamin A and are essentially in good health, suggesting that there are compensatory transport mechanisms for vitamin A that are yet undescribed. This has also been confirmed in TTR knockout mice, which do not exhibit any manifestations of vitamin A deficiency, with vitamin A uptake by most tissues continuing in the absence of RBP. Provided there is adequate vitamin A in the diet, tissue stores of vitamin A should not be affected by the

lowering of TTR and RBP. However, as the vitamin A content of the diet may vary between different countries and different individuals within a country, all patients on the study will be asked to take a supplement containing the recommended daily allowance of vitamin A. Furthermore, the safety of lowering vitamin A through TTR suppression has been further confirmed by the absence of any vitamin A deficiency-related AEs in NHPs, healthy volunteers, and patients with FAP treated with patisiran (another RNAi therapeutic with an siRNA targeting TTR formulated in a lipid nanoparticle) who experienced >80% lowering of both TTR and vitamin A. Periodic eye exams are planned for patients in this study to assess any potential impact of vitamin A lowering.

Please see the ALN-TTRSC IB for expanded risk/benefit assessment.

2. STUDY OBJECTIVES

2.1. Primary Objective

The primary objective of the study is to determine the efficacy of ALN-TTRSC in patients with FAC.

This will be assessed as the difference between treatment and placebo groups at 18 months using a co-primary endpoint of: (1) change in meters in 6-MWD compared to baseline distance; and (2) percent reduction in serum TTR levels compared to baseline levels.

3. INVESTIGATIONAL PLAN

3.1. Overall Study Design

This is a multicenter, multinational, randomized, double-blind, placebo-controlled Phase 3 study designed to demonstrate the clinical efficacy and safety of ALN-TTRSC in patients with TTR mediated FAC.

Approximately 200 consented eligible patients will be randomized to receive either ALN-TTRSC or placebo at a 2:1 ratio (ALN-TTRSC to placebo) in a blinded manner as a subcutaneous administration. Treatment groups will be balanced at randomization for NYHA classification (I and II versus III), TTR mutation (V122I versus other FAC mutations), and 6-MWD (≤325 meters versus >325 meters). Patients will receive ALN-TTRSC or placebo daily for 5 days during the first week, a single dose on Day 7, and then once weekly for 18 months.

Patients will undergo efficacy and safety assessments at Screening/Baseline, each month for first 3 months, and then at 3-6 month intervals.

The duration of patient participation in this study is approximately 20 months (inclusive of up to a 45 day Screening/Baseline window and up to 35 days of follow-up after the last dose).

3.2. Number of Patients

Approximately 200 patients will be enrolled in this study.

3.3. Efficacy Endpoints

3.3.1. Primary endpoints:

The co-primary endpoints of the study are to evaluate the difference between the ALN-TTRSC and placebo groups for:

- 1. Change in 6-MWD at 18 months compared to baseline
- 2. Percent reduction in serum TTR burden over 18 months

3.3.2. Secondary endpoints:

The secondary endpoints of the study are to determine the effect of ALN-TTRSC on various clinical parameters by assessing the difference between the ALN-TTRSC and placebo groups at 18 months for:

- Composite CV mortality and CV hospitalization
- Change in New York Heart Association (NYHA) class (Appendix 1) compared to baseline
- Change in Kansas City Cardiomyopathy Questionnaire (KCCQ) compared to baseline
- Cardiovascular (CV) mortality
- CV hospitalization

Confidential

All-cause mortality

3.3.3. Exploratory endpoints:

The exploratory endpoints of the study are to determine the difference between the ALN-TTRSC and placebo groups in the change from baseline at 18 months in the following measurements:

- EuroQOL (EQ-5D) questionnaire
- Echocardiogram parameters
- Karnofsky Performance Status (Appendix 2)
- Troponin T and I, and N-terminal prohormone of B-type natriuretic peptide (NT proBNP) levels
- Cardiac magnetic resonance imaging (CMR) parameters (only at selected sites)
- 99m Technetium scintigraphy parameters (only at selected sites)
- Amyloid in abdominal wall fat pad aspirates
- Polyneuropathy Disability (PND) Score (Appendix 3)
- Modified body mass index (mBMI)
- Estimated glomerular filtration rate (eGFR)
- HF hospitalization

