- t The 6-MWT will be conducted twice during the Screening/Baseline visit (practice and actual test to be performed at least 1 hour apart) and both tests must be completed within 28 days of Day 0. The assessments will include pre- and post-walk assessment of O₂ saturation, blood pressure, heart rate, and the Borg scale ratings for fatigue and dyspnea. The higher of the 2 values at Screening/Baseline will be used for eligibility purposes. The 6-MWT will be conducted only once, prior to dosing, at all subsequent time points.
- u An ECHO done at Screening/Baseline and for all subsequent time points will be evaluated by a central laboratory.
- v Cardiac MRI with late gadolinium enhancement (LGE) is only to be obtained in patients without contraindications (i.e., pacemakers, defibrillators, inadequate renal function or allergy to gadolinium) at selected sites on a subset of patients (up to 60). All time points will be evaluated by a central lab.
- w ^{99m}Tc scintigraphy by 3D SPECT during the study is an exploratory assessment and is not intended for diagnostic purposes or to fulfill eligibility criteria for the study. Either ^{99m}Tc pyrophosphate (^{99m}Tc-PYP) or ^{99m}Tc-3,3-diphosphono-1,2-propanodicarboxylic acid (^{99m}Tc-DPD) can be used as a tracer. The tracer should not be changed for the patient during the study. This assessment will only be performed at selected sites on a subset of patients (up to 60). All time points will be evaluated by a central lab.
- x This assessment is voluntary and will only be performed at selected sites. Additional time points may not be collected depending on the status of the Screening/Baseline biopsy sample. Repeat Screening/Baseline biopsy samples may be collected if the initial sample is not of sufficient quality.
- y Patients enrolling in the open-label extension study (ALN-TTRSC-006) will not need to complete the Month 19 visit. For these patients, Month 18 assessments will constitute the End of Study assessments.
- z Serum chemistry (including LFTs) and coagulation tests are to be performed at Week 17 and Week 21.

aa Serum SPEP with IFE, urine SPEP with IFE and serum FLC is to be performed at Screening/Baseline. If available, documented local results obtained within 1 year of Screening/Baseline may be used to fulfill this requirement.

bb These assessment will only be performed for patients enrolling in the ALN-TTRSC-006 study.

TABLE OF CONTENTS

STUDY	SYNOPSIS	3
TABLE (OF CONTENTS	15
LIST OF	TABLES	20

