7.3. Efficacy Assessments

7.3.1. Six-Minute Walk Test

The 6-MWT will be administered by staff trained in the procedure included in the Site Operation Manual. The staff administering the 6-MWT will be different from the Investigator or designee managing the care of the patient.

The 6-MWT will be performed to assess functional exercise capacity and will include pre- and post-walk assessment of O₂ saturation, blood pressure, heart rate, and the Borg scale rating for dyspnea and fatigue. The Screening/Baseline visit assessment will include a practice and an actual 6-MWT at least 1 hour apart and must be done within 28 days prior to randomization. The higher of the two values at Screening/Baseline visit will be used for eligibility purposes. At all other visits, the test should be performed only once at approximately the same time of the day. On dosing days, including Day 0, the 6-MWT should be performed prior to study drug administration. Patients who are hospitalized during the course of the study should wait at least two weeks after hospitalization before completing a 6-MWT assessment.

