6 DATA HANDLING

6.1 Time Points and Visit Windows

Day 1 will be defined as the day of first dose of study drug.

An evaluation date will be calculated relative to Day1 as follows:

- RelDay = (date of assessment date of first dose + 1) if collected after Day 1.
- RelDay = (date of assessment date of first dose) if collected prior to Day 1.

For analysis by visit, analysis windowing will be utilized for each scheduled visit such that unscheduled visits will also be considered. If there is more than one value within a visit window then the visit closest to the target day of the visit will be used in the analysis. If measurements are equally distant to the target day, then the later one will be used in the analysis. Details regarding the definition of the visit window will be summarized in a separate specifications document.

Baseline Definitions:

- For 6-MWD, baseline will be defined as the latest value prior to the first dose. If Day 1 assessment is not available, then the latest of the 2 screening 6MWD results will be selected to represent the baseline value for the patient in the analysis.
- For each of the PD parameters, baseline will be defined as the average of all measurements collected prior to the date of the first dose of study drug.
- For all other parameters, the baseline will be defined as the last assessment prior to the first dose
 of study drug.

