The time of loss of ability to perform 6-MWD will be based upon the analysis visit. A patient may have more than one onset time for loss of ability to perform 6-MWD during the study. For a patient with more than one scheduled visit where the patient was unable to perform the test, the time of loss will be at the visit where the patient lost and never regained the ability to walk. For a patient not considered to have lost the ability to walk, the time from loss of ability (censoring time) will be calculated as: (date of the latest 6MWD – date of first dose +1)/30.4. Time from first dose to loss of ability will allow values up to Month 18 analysis visit. Note: Any patient that is able to perform the walk at Month 18 visit will be considered a censored patient.

Comparison can be made if:

- Both patients indicated a loss of ability and there is no tie in the time to loss (scheduled visit)
- One patient indicated a loss of ability and the other did not, and the time of the patient who lost the ability to perform the test was \leq the time of the patient who did not lose the ability to perform the test (censoring time).

Comparison will be inconclusive if:

- Both patients indicated a loss of ability and there is a tie in the time to loss (scheduled visit)
- Both patients did not indicate a loss of ability
- One patient indicated a loss of ability and the other patient did not, and the time of the patient who lost the ability to walk > the time of the patient who did not lose the ability to walk (censoring time).

Step 3: Comparison based on change from baseline in 6-MWD

Definition of change from baseline in 6-MWD: Change in 6-MWD (meters) from baseline will be calculated as: (distance walked at post-baseline visits - distance walked at baseline). Baseline will be defined as stated in section 6.1.

To compare change from baseline in 6-MWD (meters) for a pair of patients, the latest common postbaseline study visit that both patients had 6-MWD measurements will be compared. In the event that the change in distance walked from baseline between the pair of patients is identical, a score of 0 (inconclusive) will be assigned to both patients.

Additional details:

- If a patient had > 0 meters for 6-MWD at month 18 and the patient died within month 18 analysis window, then the patient will be considered unable to perform 6-MWD at month 18.

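### The 6-MWD baseline is a single walk although two non-practice walks precede dosing, so avoidable measurement error enters the walk co-primary and costs a little power

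*Protocol*

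**What the plan says.** The endpoint in Protocol 3.3.1 is "Change in 6-MWD at 18 months compared to baseline"; that line does not say which pre-dose walk is the baseline. The rule that governs is in SAP 6.1: "For 6-MWD, baseline will be defined as the latest value prior to the first dose". The fallback is also one walk: "If Day 1 assessment is not available, then the latest of the 2 screening 6MWD results will be selected to represent the baseline value". (SAP Day 1 is the day of first dose, which the protocol calls Day 0.)

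Three walks precede dosing. Protocol Table 1-1, footnote t, says: "The 6-MWT will be conducted twice during the Screening/Baseline visit (practice and actual test to be performed at least 1 hour apart", both within 28 days of Day 0. Table 1-1 also schedules a Day 0 pre-dose walk, and Protocol 7.3.1 confirms it: "On dosing days, including Day 0, the 6-MWT should be performed prior to study drug administration".

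SAP Appendix I, Step 3, scores the raw difference: "Change in 6-MWD (meters) from baseline will be calculated as: (distance walked at post-baseline visits - distance walked at baseline". It refers back to SAP 6.1 for the baseline. The joint rank test has no baseline covariate. SAP 7.6 stratifies it by TTR mutation and by 6-MWD at a 325 m cut.

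**The concern.** A walk distance varies from test to test in the same patient. When change is measured from one walk, all of that error goes into the change score. When it is measured from the mean of two walks with independent errors, half of the baseline error variance drops out. The second walk is already in the database.

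The walk test is the co-primary that limits power: Protocol 9.1 puts power for serum TTR above 90% and overall power at about 90%. With about 200 patients at about 60 sites in a rare disease, precision that needs no new test or visit is worth having. The same choice of baseline also feeds the descriptive change summaries and the mixed-model sensitivity analysis.

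**Working it through.** **Inputs from the documents** (Protocol 9.1; SAP 2.3): 120 vs 60 patients; effect 0.55 SD; SD of change 70 m, so 0.55 × 70 = 38.5 m, given as 39 m; deaths by 18 months 13% on active and 20% on placebo; two-sided 0.05; Finkelstein-Schoenfeld test; stated power 90%.

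**Assumed, because no document gives it:** the within-patient test-retest SD of a walk, s, taken as 10 to 40 m.

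**1. Reproduce the plan's figure.** Simulation of 40,000 trials used exponential death times matching 13% and 20%, normal change in survivors, deaths ranked by time below all survivors, and no loss of walking ability. Power was 88.3% at 0.55 SD and 89.0% at 39/70 SD. With four equal strata (the number that the two SAP 7.6 factors create) it was 87.9% and 88.5%. The stated 90% is reproduced to within about 2 points.

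**2. Share of comparisons affected.** If only deaths decide earlier steps, 0.87 × 0.80 = 0.696, so about 70% of between-arm pairs reach Step 3.

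**3. Effect of averaging.** Let ρ be the correlation between the errors of the two baseline walks. One walk contributes error variance s²; the mean of two contributes s²(1 + ρ)/2. The reduction is s²(1 − ρ)/2, so

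SD of change = √(70² − s²(1 − ρ)/2).

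For s = 30 m and ρ = 0: √(4900 − 450) = 66.7 m. Rerunning the unstratified simulation with the effect fixed at 38.5 m, from the base of 88.3%:

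| Assumed s | SD of change, ρ = 0 | Power, ρ = 0 | Gain, ρ = 0 | Gain, ρ = 0.5 |
|---|---|---|---|---|
| 10 m | 69.6 m | 88.6% | +0.3 points | +0.1 |
| 20 m | 68.6 m | 89.4% | +1.0 | +0.5 |
| 30 m | 66.7 m | 90.6% | +2.3 | +1.1 |
| 40 m | 64.0 m | 92.3% | +4.0 | +2.0 |

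Gains are taken before rounding. They are the same with four strata, but those strata were equal splits that carried no information on walk distance.

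**4. Drift between the two walks.** Protocol 1.4 expects a decline of 74 to 118 m in 18 months (78 weeks, 546 days). Over 28 days that is 74 × 28/546 = 3.8 m to 118 × 28/546 = 6.1 m on average. A common shift adds no variance and is the same in both arms. A lasting shift that differs between patients does add variance. If its SD is d, independent of later decline, the variance of change becomes

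4900 − s²/2 + d²/4.

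At d = s the reduction is s²/4, half of the full gain. It reaches zero when d²/4 = s²/2, that is d = 1.41s (28 m when s = 20 m).

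**5. Loss of walking ability.** With a 10% loss at Step 2 in each arm, 0.696 × 0.9 × 0.9 = 0.564, so about 56% of between-arm pairs reach Step 3. Simulated gains of about 1, 2 and 4 points for s = 20, 30 and 40 m persist in that setting.

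**6. What 70 m refers to.** The documents do not say whether 70 m describes change from one walk or from an average. If it already described an averaged baseline, the single-walk rule would give 88.1%, 87.4%, 86.1% and 84.6% for s = 10, 20, 30 and 40 m.

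**The case against.** The SAP rule is clear, set in advance, has a fallback, and matches its rule for most other parameters. If 70 m is the SD of change from a single walk, the noise is already inside the stated power and the plan delivers what it claims. That stands: this is a choice about efficiency.

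The two walks may not be exchangeable. The actual screening walk follows a practice walk, perhaps by only an hour, and can be up to 28 days older. It also bears on eligibility at 150 m, so it is subject to selection. Day 0 and all follow-up walks are done once, so Day 0 matches follow-up conditions better. That the shift is equal in both arms answers bias, not variance. This also stands, and it is why the gain is given with correlation and drift included. Neither s nor d is documented.

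Two stronger readings are tempting and do not hold:

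- A reader might infer that the screening walk is thrown away. It is not. Protocol 1.4 uses screening 6-MWD for the stratification factor, SAP 7.6 stratifies the analysis on 6-MWD, and the mixed-model sensitivity analysis includes the screening value. It is only left out of the baseline that Step 3 subtracts.
- A reader might infer that SAP 6.1 contradicts itself, since for PD parameters "baseline will be defined as the average of all measurements collected prior to the date of the first dose of study drug". The contrast is weak. Table 1-1 schedules serum TTR only at the Day 0 pre-dose time point, with no screening sample, so for the co-primary PD measure there is normally little to average.

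**Conclusion.** The point holds as a modest loss of precision. The baseline is one walk, a second usable walk exists, and Step 3 carries the full error of the first. Averaging adds about 0.3 to 4 points of power for s = 10 to 40 m with independent errors, and about 1 to 2 points in the middle of that range. The gain is roughly half that at an error correlation of 0.5, or when patient-specific drift has an SD equal to s. It is nil once the drift SD reaches 1.41s.

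The size rests on an assumed retest SD, on normal change in survivors, and on 70 m being the SD from a single-walk baseline. Only the baseline part of the noise is reduced; error in the month 18 walk and true variation in decline remain.

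A reader might infer that the walk comparison is biased or that the 90% figure is wrong. The documents support neither: both pre-dose walks precede study treatment in both arms, and the stated power is reproduced to within about 2 points under the plan's own assumptions.

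**What to change.** In SAP 6.1, define baseline 6-MWD as the mean of the actual (second, non-practice) screening walk and the Day 0 pre-dose walk. If only one of these is available, use that one. Leave the practice walk out. Keep the latest-value baseline as a sensitivity analysis of the joint rank test. Eligibility and stratification rules do not change. Appendix I takes its baseline from SAP 6.1, so Step 3 follows without further editing.

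Make the change before any unblinding, including the optional futility analysis. SAP 7.8 already foresees an update for the futility criteria, and Protocol 9.2 requires the SAP to be final before database lock, so there is an occasion for it. Because patients have already been treated (83 as of 14 January 2016, Protocol 1.3), record that the decision was made blind.

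The cost is one sentence and no new test or visit. The downsides are small: learning or short-term drift between screening and Day 0 enters the baseline, the same in both arms, and patients with only one walk have a noisier baseline than the rest. Before adopting it, the sponsor can check the blinded, pooled differences between the two walks. For independent errors and patient-specific drift their variance is 2s² + d², which shows how far the walks disagree, although it does not separate s from d.

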3.4. Safety Assessments

Safety will be assessed throughout the study by collecting adverse events (AEs; including serious adverse events [SAEs]); clinical laboratory safety tests including, hematology, serum chemistry (including liver function tests), thyroid function, coagulation, vitamin A, and urinalysis; measurement of anti-drug antibodies; electrocardiograms; vital signs; physical examination findings; and ophthalmology examinations.

